9. STATISTICAL METHODOLOGY

9.1 General

Data listings will be provided for all data that is databased. Summary statistics and statistical analysis will only be presented for data where detailed in this SAP. For continuous data, summary statistics will include the arithmetic mean, arithmetic SD, median, min, max and N; for log-normal data (e.g. the PK parameters: area under the concentration versus time curve [AUCs] and C_{max}) the geometric mean and geometric coefficient of variation (CV%) will also be presented. For categorical data, frequency count and percentages will be presented. Data listings will be provided for all subjects up to the point of withdrawal, with any subjects excluded from the relevant population highlighted. Summary statistics and statistical analyses will generally only be performed for subjects included in the relevant analysis population. For the calculation of summary statistics and statistical analysis, unrounded data will be used.

Mean change from baseline is the mean of all individual subjects’ change from baseline values. Each individual change from baseline will be calculated by subtracting the individual subject’s baseline value from the value at the timepoint. The individual subject’s change from baseline values will be used to calculate the mean change from baseline using a CCI procedure such as CCI.

Data analysis will be performed using C or greater.

9.2 Demographics and Subject Disposition

Subject disposition will be listed. The demographic variables age, sex, race, ethnicity, body weight, height, body mass index, and hip and waist circumference will be summarized and listed.

9.3 Pharmacokinetic Analyses

9.3.1 Pharmacokinetic Parameter Estimation

Subjects who completed at least 1 period and had evaluable insulin lispro concentrations will be included in the PK analysis dataset. PK analyses will be conducted using standard noncompartmental methods of analysis using **CCI** on a computer that meets or exceeds the minimum system requirements for these programs. The version of any software used for the analysis will be documented and the program will meet the Lilly requirements of software validation. It is possible that other validated equivalent PK software programs may be utilized if appropriate, warranted, and approved by global PK management.

Free serum insulin lispro concentrations will be used to calculate several PK parameters, including C_{max} , time of maximum observed drug concentration (t_{max}), time to early half-maximal drug concentration (early 50% t_{max}), time to late half-maximal drug concentration (late 50% t_{max}), and $AUC([0-t_{last}])$, area under the concentration versus time curve from time zero to 10 hours ($AUC[0-10h]$), and $AUC(0-\infty)$. Other parameters may be calculated as deemed appropriate, such as partial AUCs.

Although attempts will be made to adhere to the scheduled collection times, it is recognized that situations arise that may compromise the scheduled times. Parameters will be individually calculated for each subject based on actual collection times and presented by summary statistics.

9.3.2 Pharmacokinetic Statistical Inference

To compare PK parameters between LY900014 U-200 relative to LY900014 U-100, log-transformed AUC parameter estimates ($AUC[0-t_{last}]$, $AUC[0-\infty]$) and C_{max} will be analyzed using the mixed-effects model that includes treatment, sequence, and period as fixed effects and subject within sequence as a random effect. From the model, the difference in LSmeans and the corresponding 2-sided 90% CIs for the difference will be estimated and back-transformed from the log scale to provide estimates of the ratio of geometric LSmeans and 90% CI for the ratio of the LSmeans. Bioequivalence will be concluded if the 2-sided 90% CI is completely contained within the interval (0.80, 1.25).

Example **CCI** code:

```
proc mixed data=pk;
class patient period treatment sequence ;
model logpk = treatment period sequence / ddfm=kr alpha=0.1;
random patient(sequence);
lsmeans treatment;
run;
```

In addition, the same model without log transformation will be used for the analysis of the PK time parameters (early 50% t_{max} , and t_{max}). LSmeans, treatment differences in LSmeans, and the corresponding 90% CIs for the treatment differences will be estimated from the model. The treatment ratios and 90% CIs for the ratios will be calculated using Fieller's theorem. As a sensitivity analysis, the PK time parameters will be analyzed nonparametrically using Wilcoxon signed rank test.

In addition, the analyses described above will also be performed on the population of subjects who completed and had evaluable PK data in all study periods.

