6. TREATMENTS

The following is a list of the study treatment abbreviations that will be used in the TFLs.

Study Treatment Name	Treatment order in TFL
15 U LY900014 U-100 SC	1
15 U LY900014 U-200 SC	2

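### Does the example model code in SAP 9.3.2 put the 90% confidence interval for the primary bioequivalence test at risk?

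*SAP*

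**What the plan says.** The purpose given in SAP 9.3.2 is "To compare PK parameters between LY900014 U-200 relative to LY900014 U-100". The method text continues: "From the model, the difference in LSmeans and the corresponding 2-sided 90% CIs for the difference will be estimated". The result is back-transformed to a ratio, and bioequivalence is concluded if the 2-sided 90% CI lies wholly inside 0.80 to 1.25. Protocol 10.3.2.2 and the protocol synopsis state the same level and rule. SAP 7 and protocol 10.1 power the study on 90% CIs.

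Below that text, SAP 9.3.2 prints a short block introduced as example code:

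- The procedure line, "proc mixed data=pk", carries no alpha setting.
- The model line is "model logpk = treatment period sequence / ddfm=kr alpha=0.1", without a request for the fixed-effect solution or its limits.
- The last working line is "lsmeans treatment", without options.
- There is no ESTIMATE or CONTRAST statement.

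SAP 9.4.2 describes the same model for Gtot and Rmax and states its own 90% level. It prints no code. SAP 6 lists treatment labels for the tables, figures and listings, the first being "15 U LY900014 U-100 SC".

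**The concern.** Run as printed, the block gives two treatment LSmeans. It gives no difference and no interval for one, yet that interval is what the primary decision uses. The alpha of 0.1 suggests that the author meant to obtain 90% limits. On the MODEL statement it governs limits for the fixed-effect estimates, which the block does not request, so it affects no treatment comparison.

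The worry is the repair. A programmer who finds the comparison missing may add the difference and confidence-limit options to LSMEANS and assume that the alpha already in the code applies. If LSMEANS keeps its own default of 0.05, the output is a 95% CI from code that still shows 0.1. That would be a test at 2.5% per side where 5% is planned, with a loss of power on every parameter analysed this way. A default difference might also be taken as U-100 minus U-200, which inverts the reported ratio.

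**Working it through.** **Text against code.**

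| Item | Text of SAP 9.3.2 | Example code |
|---|---|---|
| Model terms | treatment, sequence, period fixed; subject within sequence random | same |
| Comparison | U-200 relative to U-100 | not requested |
| Interval | 2-sided 90% | not requested |
| Decision | inside 0.80 to 1.25 | not applicable |

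The code leaves out two outputs that the text specifies. It contradicts nothing in the text.

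**Inputs for the size of a slip.** N = 44 completers. Stated power is at least 95% for AUC (up to 5% difference) and Cmax (10% difference), and at least 85% for Gtot and Rmax (up to 10% difference), all from SAP 7. The SDs are redacted, so the stated power cannot be reproduced. I assume instead the largest standard error (SE) that just meets each stated power. Residual df are 4 × 44 − 44 − 4 = 128, with 44 − 4 = 40 as a variant. That LSMEANS limits default to alpha 0.05 is taken as software behaviour; the documents do not state it.

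**Interval width.** Half-width on the log scale is t × SE.

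- df 128: t = 1.657 for 90% and 1.979 for 95%; ratio 1.194.
- df 40: t = 1.684 and 2.021; ratio 1.200.

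**Power.** Power is the probability that estimate ± t × SE lies between ln 0.80 and ln 1.25, with the variance integrated over its chi-square distribution. SD = SE × √44. Ranges run over df 40 and 128.

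| Parameter | True ratio | Largest SE | SD | Power, 90% CI | Power, 95% CI |
|---|---|---|---|---|---|
| AUC | 0.95 | 0.0513-0.0519 | 0.340-0.345 | 95% | 90.4-90.7% |
| Cmax | 0.90 | 0.0352-0.0356 | 0.233-0.236 | 95% | 90.4-90.7% |
| Gtot, Rmax | 0.90 | 0.0432-0.0437 | 0.286-0.290 | 85% | 75.9-76.3% |

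These are worst cases, because the plan says at least. Solving for the SD at which a 95% CI still meets the stated power gives 0.308-0.314 for AUC and 0.211-0.215 for Cmax, about 9% below the maximum. For Gtot and Rmax the reduction needed is about 11%. With SDs 20% below the maximum, AUC and Cmax power goes from 99.3% to 98.3-98.4%, and Gtot and Rmax power from 95.6% to 91.4-91.7%. All of these exceed the stated floors.

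**When the verdict would differ.** The 90% CI passes and the 95% CI fails when the SE lies between d/t95 and d/t90, where d is the log distance from the observed ratio to the nearer limit. For an observed ratio of 0.90, d = ln(0.90/0.80) = 0.1178. With df 128 the range is 0.1178/1.979 = 0.0595 to 0.1178/1.657 = 0.0711. The Cmax design needs an SE of at most 0.0356, and 0.0595/0.0356 = 1.67. At the assumed ratio, the verdict would change only if the SE were at least 1.67 times the design maximum. A more extreme observed ratio would bring that range down.

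**Direction.** The limits are reciprocal (1/0.80 = 1.25), so inverting the ratio, for example 0.90 to 1/0.90 = 1.11, leaves pass or fail unchanged.

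**The case for a change.** The strongest case for acting is that code printed to implement the primary analysis ought to produce the primary result. This is the only model code in the SAP. The alpha on the MODEL line gives false reassurance, so a reviewer could pass a 95% interval as a 90% one. A repair takes two lines and needs no protocol amendment.

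The description of the code stands in full. The consequence does not follow:

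- The block yields no interval at all, so nobody can run it and accept a wrong answer unawares. Someone must add the comparison, and the sentence they work from reads "the difference in LSmeans and the corresponding 2-sided 90% CIs for the difference will be estimated". A 95% interval would contradict that sentence, the protocol and the sample-size section. SAP 3 requires substantial deviations from the SAP to be agreed and identified in the study report.
- The error would be conservative. A wider interval cannot raise the chance of a false bioequivalence claim.
- Carry-over to Gtot and Rmax is conjecture, since SAP 9.4.2 states its own 90% level. It also sets no pass or fail rule for them.
- The reversed sign is not established. The labels in SAP 6 are for the outputs, and the coding of the treatment variable in the analysis dataset is not given.

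**Conclusion.** This is a clerical gap in example code, and no change to the plan is needed. The text of SAP 9.3.2 settles the comparison, its direction, the 90% level and the decision rule, and an analyst who follows it reaches the planned result whatever the sample code omits. Completing the code would alter no planned estimate, interval or conclusion.

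The possible cost is bounded. It arises only if a programmer adds limits at the software default and nobody compares the output with the text. The loss is then at most about 4 to 5 percentage points of power for AUC and Cmax, and about 9 points for Gtot and Rmax, in the conservative direction. Those figures assume 44 completers, SDs at the largest values compatible with the stated power, and df between 40 and 128. With SDs about 9% (AUC, Cmax) or 11% (Gtot, Rmax) smaller, the stated power survives the slip.

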9.4 Pharmacodynamic Analyses

9.4.1 Pharmacodynamic Parameter Estimation

GD assessments will be determined from the glucose clamp procedure, where the glucose infusion rate (GIR) over time will be used as a measure of insulin effect. GD analyses will be conducted on those subjects who complete at least 1 clamp procedure.

A locally weighted scatterplot smoothing (LOESS) function will be applied to all individual GIR versus time profiles in each treatment group and/or period using S-PLUS software (version 8.2). The fitted data for each subject will be used to calculate the following GD parameters: time to onset of insulin action (tonset), time to maximal GIR (R_{max}), time to R_{max} (tR_{max}), time to half-maximal GIR before tR_{max} (early 50% tR_{max}), and total amount of glucose infused (G_{tot}). Additional partial glucose AUCs, may be computed as necessary. The values of these GD parameters will be summarized by treatment and/or period through descriptive statistics. Mean LOESS fits of GIR versus time profiles will be generated.

9.4.2 Pharmacodynamic Statistical Inference

To address the secondary objective of comparing GD parameters (G_{tot} and R_{max}) between the LY900014 U-200 and LY900014 U-100 formulations, log-transformed G_{tot} and R_{max} estimates will be analyzed using the mixed-effects model that includes treatment, sequence, and period as fixed effects and subject within sequence as a random effect. From the model, the difference in LSmean estimates and the corresponding 90% for the difference will be estimated and back-transformed from the log scale to provide estimates of the ratios of geometric LSmeans and 90% for the ratio of the LSmeans. For GD parameters that have at least 1 patient with a value equal to zero, an analysis of original scale data (not log-transformed) will be performed as described below for the GD time parameters.

In addition, the same model without log transformation will be used for the analysis of the GD time parameters (tR_{max} and early 50% tR_{max}). LSmeans, treatment differences in LSmeans, and the corresponding 90% CIs for the treatment differences will be estimated from the model. The p-value for the difference between LSmeans will be used to determine statistical significance. The treatment ratios and 90% CIs for the ratios will be calculated using Fieller's theorem. Other GD time parameters may be analyzed in a similar manner. As a sensitivity analysis, the GD time parameters will be analyzed nonparametrically using Wilcoxon signed rank test.

In addition, the analyses described above will also be performed on the population of subjects who completed and had evaluable GD data in all study periods.

9.5 Safety and Tolerability Assessments

9.5.1 Adverse events

Where changes in severity are recorded in the Case Report Form (CRF), each separate severity of the AE will be reported in the listings, only the most severe will be used in the summary tables. A pre-existing condition is defined as an AE that starts before the subject has provided written informed consent and is ongoing at consent. A non-treatment emergent AE is defined as an AE which starts after informed consent but prior to dosing. A treatment-emergent AE is defined as an AE which occurs postdose or which is present prior to dosing and becomes more severe postdose.

All AEs will be listed. Treatment-emergent AEs will be summarized by treatment, severity and relationship to the study drug. The frequency (the number of AEs, the number of subjects experiencing an AE and the percentage of subjects experiencing an AE) of treatment-emergent AEs will be summarized by treatment, Medical Dictionary for Regulatory Activities (MedDRA) version 20.0 system organ class and preferred term. The summary and frequency AE tables will be presented for all causalities and those considered related to the study drug. Any serious AEs will be tabulated.

9.5.2 Concomitant medication

Concomitant medication will be coded using the WHO drug dictionary (Version March 2017). Concomitant medication will be listed.

9.5.3 Clinical laboratory parameters

All clinical chemistry, hematology and urinalysis data will be listed. Additionally clinical chemistry, hematology and urinalysis data outside the reference ranges will be listed.

Values for any clinical chemistry, hematology and urinalysis values outside the reference ranges will be flagged on the individual subject data listings.

9.5.4 Vital signs

Vital signs data will be summarized by treatment together with changes from baseline, where baseline is defined as Day 1 predose.

Furthermore, values for individual subjects will be listed.

9.5.5 Blood Glucose Monitoring and Hypoglycemia

Hypoglycemic events will be appropriately recorded in the CRF. In the case of a hypoglycemic event, the actual blood glucose value, if measured, will be recorded in the CRF, together with

any treatments administered. Each category of hypoglycemic events (defined below) will be listed and summarized by treatment.

Hypoglycemia is defined as follows:

- **Documented Glucose Alert Level (Level 1), Plasma Glucose (PG) ≤ 70 mg/dL (3.9 mmol/L):**
 - **Symptomatic hypoglycemia:** an event during which typical symptoms of hypoglycemia are accompanied by plasma glucose ≤ 70 mg/dL (3.9 mmol/L)
 - **Asymptomatic hypoglycemia:** an event not accompanied by typical symptoms of hypoglycemia but with plasma glucose ≤ 70 mg/dL (3.9 mmol/L)
 - **Unspecified hypoglycemia:** an event during which plasma glucose ≤ 70 mg/dL (3.9 mmol/L) but with no available information related to symptoms of hypoglycemia
- **Probable symptomatic hypoglycemia:** an event during which symptoms indicative of hypoglycemia are observed but not accompanied by a plasma glucose determination (but that was presumably caused by plasma glucose ≤ 70 mg/dL [3.9 mmol/L])
- **Documented Clinically significant hypoglycemia (Level 2) PG < 54 mg/dL (3.0 mmol/L):**
 - **Symptomatic hypoglycemia:** an event during which typical symptoms of hypoglycemia are accompanied by PG ≤ 54 mg/dL (3.0 mmol/L)
 - **Asymptomatic hypoglycemia:** an event not accompanied by typical symptoms of hypoglycemia but with PG ≤ 54 mg/dL (3.0 mmol/L)
 - **Unspecified hypoglycemia:** an event during which PG ≤ 54 mg/dL (3.0 mmol/L) but no information relative to symptoms of hypoglycemia was recorded.
- **Severe hypoglycemia (Level 3):** an event during which patients had altered mental status, and could not assist in their own care, or were semiconscious or unconscious, or experienced coma with or without seizures, and the assistance of another person was to actively administer carbohydrate, glucagon, or other resuscitative actions. Plasma glucose measurements may not be available during such an event, but neurological recovery attributable to the restoration of plasma glucose to normal is considered sufficient evidence that the event was induced by a low plasma glucose concentration (≤ 70 mg/dL [3.9 mmol/L]).
 - **Severe hypoglycemia requiring medical attention:** a severe hypoglycemic event when patients require therapy by HCPs (EMTs, emergency room personnel, etc.).
- **Nocturnal hypoglycemia:** any hypoglycemic event (documented symptomatic, asymptomatic, probable symptomatic, or severe hypoglycemia) that occurs between bedtime and waking
- **Relative hypoglycemia:** an event during which typical symptoms of hypoglycemia, that do not require the assistance of another person, are accompanied by plasma glucose > 70 mg/dL (3.9 mmol/L), but these levels may be quickly approaching the 70 mg/dL (3.9 mmol/L) threshold

Overall (or total) hypoglycemia: This optional category combines most cases of hypoglycemia except relative hypoglycemia. Nocturnal and severe hypoglycemia are special cases of documented or probable hypoglycemia. If an event of hypoglycemia falls into multiple subcategories, that event should be counted only once in this category of overall (or total) hypoglycemia

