#### 9.4.5.1. Glucose Monitoring

Hypoglycemia will be described using the following definitions:

- **Documented Glucose Alert Level (Level 1), Plasma Glucose (PG)  $\leq 70$  mg/dL (3.9 mmol/L):**
  - **Symptomatic hypoglycemia:** an event during which typical symptoms of hypoglycemia are accompanied by plasma glucose  $\leq 70$  mg/dL (3.9 mmol/L)
  - **Asymptomatic hypoglycemia:** an event not accompanied by typical symptoms of hypoglycemia but with plasma glucose  $\leq 70$  mg/dL (3.9 mmol/L)
  - **Unspecified hypoglycemia:** an event during which plasma glucose  $\leq 70$  mg/dL (3.9 mmol/L) but with no available information related to symptoms of hypoglycemia
- **Probable symptomatic hypoglycemia:** an event during which symptoms indicative of hypoglycemia are observed but not accompanied by a plasma glucose determination (but that was presumably caused by plasma glucose  $\leq 70$  mg/dL [3.9 mmol/L])
- **Documented Clinically significant hypoglycemia (Level 2) PG  $< 54$  mg/dL (3.0 mmol/L):**
  - **Symptomatic hypoglycemia:** an event during which typical symptoms of hypoglycemia are accompanied by PG  $\leq 54$  mg/dL (3.0 mmol/L)
  - **Asymptomatic hypoglycemia:** an event not accompanied by typical symptoms of hypoglycemia but with PG  $\leq 54$  mg/dL (3.0 mmol/L)
  - **Unspecified hypoglycemia:** an event during which PG  $\leq 54$  mg/dL (3.0 mmol/L) but no information relative to symptoms of hypoglycemia was recorded.
- **Severe hypoglycemia (Level 3):** an event during which patients had altered mental status, and could not assist in their own care, or were semiconscious or unconscious, or experienced coma with or without seizures, and the assistance of another person was to actively administer carbohydrate, glucagon, or other resuscitative actions. Plasma glucose measurements may not be available during such an event, but neurological recovery attributable to the restoration of plasma glucose to normal is considered sufficient evidence that the event was induced by a low plasma glucose concentration ( $\leq 70$  mg/dL [3.9 mmol/L]).
  - **Severe hypoglycemia requiring medical attention:** a severe hypoglycemic event when patients require therapy by HCPs (EMTs, emergency room personnel, etc.).
- **Nocturnal hypoglycemia:** any hypoglycemic event (documented symptomatic, asymptomatic, probable symptomatic, or severe hypoglycemia) that occurs between bedtime and waking

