- **Relative hypoglycemia:** an event during which typical symptoms of hypoglycemia, that do not require the assistance of another person, are accompanied by plasma glucose  $> 70$  mg/dL (3.9 mmol/L), but these levels may be quickly approaching the 70 mg/dL (3.9 mmol/L) threshold
- **Overall (or total) hypoglycemia:** This optional category combines most cases of hypoglycemia except relative hypoglycemia. Nocturnal and severe hypoglycemia are

special cases of documented or probable hypoglycemia. If an event of hypoglycemia falls into multiple subcategories, that event should be counted only once in this category of overall (or total) hypoglycemia.

The goal of the euglycemic clamp is to maintain glucose concentrations at normoglycemic levels close to a predefined target. Therefore, the equivalence of plasma glucose concentrations below 70 mg/dL will not routinely be recorded as hypoglycemic events during the glucose clamp procedure. However, at the discretion of the investigator, decrease in glucose concentrations may be recorded as a hypoglycemic event based on clinical concern or related to technical issues resulting in hypoglycemia.

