The target value for blood glucose concentrations is defined as 5 mg/dL below the mean of predose fasting blood glucose concentration measured on the day of the glucose clamp. Subjects will not be clamped to a glucose target of lower than 63 mg/dL (whole blood). Therefore, subjects with a mean predose fasting blood glucose less than 68 mg/dL (equivalent to a fasting plasma glucose of 76 mg/dL [4.21 mmol/L]) will not undergo the clamp procedure but may be deferred to a later period. In addition, any study procedures conducted up to that time may be repeated in that later period.

The GIRs required to maintain target glucose levels and blood glucose concentrations will be documented throughout the procedure. Subjects will be medically assessed before discharge from the CRU (see Schedule of Activities [Section 2]).

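### Does the clash between < 54 and ≤ 54 mg/dL in the Level 2 hypoglycemia definition call for a change to the plan?

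*SAP*

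**What the plan says.** SAP section 9.5.5 defines the hypoglycemia tiers and commits to tabulating them: "Each category of hypoglycemic events (defined below) will be listed and summarized by treatment". The second tier is headed "Documented Clinically significant hypoglycemia (Level 2) PG < 54 mg/dL (3.0 mmol/L"). Its symptomatic subcategory reads "typical symptoms of hypoglycemia are accompanied by PG ≤ 54 mg/dL (3.0 mmol/L"), and the asymptomatic and unspecified subcategories use the same non-strict sign. Protocol section 9.4.5.1 has the same arrangement: a strict sign in the heading and a non-strict sign in all three lines below it.

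Level 1 is consistent in both documents, with ≤ 70 mg/dL in the heading and in every subcategory.

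Two other provisions limit how far the mismatch reaches. Protocol section 9.4.5.1 says that glucose values below 70 mg/dL "will not routinely be recorded as hypoglycemic events during the glucose clamp procedure", with discretion left to the investigator. SAP section 9.5.12 plans no inferential analysis of safety data.

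**The concern.** A classification rule should give one answer for every possible value. Here a plasma glucose of exactly 54 mg/dL gives two: outside Level 2 by the heading, inside it by the subcategories. Nothing else in the documents settles the matter:

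- The SAP supersedes the protocol's statistical considerations (SAP section 3), but both carry the same conflict.
- The count-once rule in SAP section 9.5.5 covers only the overall hypoglycemia category.
- The list of changes in SAP section 11 covers only the pain-score analysis.

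Because each category is summarized by treatment, two programmers could produce different Level 2 counts from the same data. If the group row followed the heading and the subcategory rows followed their own definitions, the subcategories could add up to more than the group. Hypoglycemia is the first potential risk named in Protocol section 3.3, and safety and tolerability is a secondary objective, so the point deserves a check.

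**Working it through.** **1. The two rules side by side (SAP section 9.5.5; Protocol section 9.4.5.1 is identical in effect).**

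| Plasma glucose (mg/dL) | Heading, < 54 | Subcategories, ≤ 54 | Level 1, ≤ 70 |
|---|---|---|---|
| 53 | yes | yes | yes |
| 54 | no | yes | yes |
| 55 | no | no | yes |

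The rules part only at 54, and an event there is kept as Level 1 under either reading.

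**2. The unit equivalence.** Both documents pair 54 mg/dL with 3.0 mmol/L. That implies 54 / 3.0 = 18.0 mg/dL per mmol/L. Protocol section 9.6 pairs 76 mg/dL with 4.21 mmol/L, which implies 76 / 4.21 = 18.05, and 54 / 18.05 = 2.99, which rounds to 3.0. The stated equivalence is reproduced.

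If values were held in mmol/L to one decimal, a recorded 3.0 would cover 2.95 × 18.0 = 53.1 up to 3.05 × 18.05 = 55.1 mg/dL across the two factors. The boundary would then be about 2 mg/dL wide rather than a single value. The documents do not say which unit is used to classify events.

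**3. How a value near 54 could arise.** Blood glucose is sampled repeatedly only for the clamp (Protocol section 2); otherwise glucose appears only in the safety chemistry panel (Protocol Appendix 2). Clamp readings are whole blood. The lowest permitted target is 63 mg/dL whole blood (Protocol section 9.6). The same section says 68 mg/dL whole blood is "equivalent to a fasting plasma glucose of 76 mg/dL [4.21 mmol/L"], a ratio of 76 / 68 = 1.1176.

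As an illustration, assume this ratio also holds at lower values:

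- 54 / 1.1176 = 48.3 mg/dL whole blood, which is 63 − 48.3 = 14.7 mg/dL below the lowest target.
- A reading of 48 converts to 48 × 1.1176 = 53.65, and 49 converts to 49 × 1.1176 = 54.76. If readings are whole numbers, neither is exactly 54; 48 becomes 54 only after rounding.

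SAP section 9.1 says "For the calculation of summary statistics and statistical analysis, unrounded data will be used", but that sentence does not explicitly cover event classification. The ratio is given only for deciding whether a clamp goes ahead, and whole-number readings are assumed. The calculation shows that boundary values should be rare; it does not prove that there are none.

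**4. What uses the Level 2 count.**

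- Bioequivalence (SAP section 9.3.2) rests on AUC(0-tlast), AUC(0-∞) and Cmax.
- The secondary glucodynamic comparison (SAP section 9.4.2) rests on Gtot and Rmax.
- The secondary safety endpoint (Protocol section 4) is adverse events.
- Discontinuation criteria (Protocol section 8) refer to liver tests and general grounds, and dose adjustment is not allowed (Protocol section 7.4).
- Severe hypoglycemia is defined by clinical state and reported as a serious adverse event (Protocol sections 9.4.5.1 and 9.4.5.1.1).

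None depends on whether an event at 54 mg/dL is counted as Level 2.

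**The case for a change.** The strongest case for acting is one of principle. The SAP is meant to be signed off before first dosing so that rules are fixed before data exist. The sponsor's study team is unblinded (Protocol section 7.3), so a boundary event would be classified afterwards by people who could know the treatment. Rarity argues for low priority, not for leaving a contradiction in place, and settling it would need no new data. The mmol/L point also shows that the boundary may be wider than a single value.

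The contradiction itself stands: it is in the current text of both documents, and no written rule resolves it. The consequence does not follow from it. The subcategory lines describe the individual events, and together they cover every documented Level 2 event according to symptom status; the heading labels the group. A programmer who builds each category from its own line and sums them gets a coherent table. That is a remark about how the text is laid out, not about which sign is clinically right. SAP section 3 also places the detail of the outputs in a separate shell document that is not available here and may already settle the sign.

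The worry about later choice is limited too. The glucose value, if measured, is recorded for each event, and all data in the database are listed (SAP sections 9.5.5 and 9.1), so a reader can see a boundary event and count it either way. One coded rule would apply to both formulations alike.

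**Conclusion.** The inconsistency is confirmed, and it is clerical. It can move only an event recorded at exactly 54 mg/dL, or at 3.0 mmol/L if values are held to one decimal, in or out of a descriptive Level 2 row. The event stays in Level 1 and can still be counted in overall hypoglycemia. The number of such events cannot be derived from the documents. It is probably very small, given that low clamp readings are not routinely recorded as events and that the value lies well below the lowest clamp target. No endpoint, test, discontinuation rule or bioequivalence decision changes under either reading.

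This rests on two assumptions: that one rule is coded for both formulations, and that boundary events are as rare as the clamp conduct suggests. If the second failed, the table would still be descriptive and the listings would show each recorded value. No amendment is warranted. Ordinary programming specifications can settle the sign and the unit, and the sponsor's clinical team can reconcile the wording if either document is reopened for another reason.
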